4 INVESTIGATIONAL PRODUCT

4.1 Investigational Product Description

AV-1

AV-1 is a fully human IgG1_K mAb that targets the conserved fusion loop structure of the virus envelope protein. AV-1's Fc portion has been engineered with leucine to alanine substitution of amino acids at positions 234 and 235 to avoid dengue antibody-dependent enhancement. Clinical doses will be prepared at the study site pharmacy in sterile 0.9% NaCl. AV-1 is being developed for treatment of dengue.

Placebo

The placebo is commercially available sterile 0.9% NaCl.

4.1.1 Formulation, Packaging, and Labeling

The AV-1 drug substance is formulated in 20 mM citrate (pH 5.6), 150 mM NaCl, and 0.025% polysorbate 80 to a nominal concentration of 25 mg/mL of the AV-1 antibody.

AV-1 will be supplied as a sterile, clear, colorless to pale yellow solution filled in a primary glass container with coated stopper and aluminum seal. The lower end of the fill volume range is controlled to ensure at least 4 mL recovery (100 mg total) from each vial during use.

The AV-1 drug product will be labeled according to manufacturer or regulatory specifications and include the statement "Caution: New Drug – Limited by Federal Law to Investigational Use."

4.1.2 Product Storage and Stability

AV-1

AV-1 must be stored in a secure area at 2°C to 8°C (36°F to 46°F). The study site pharmacy has continuous temperature monitoring with alarm notification. Vials should not be shaken.

Current stability data shows AV-1 is stable when stored at 2°C to 8°C (36°F to 46°F) for at least 18 months. Stability testing is ongoing and planned for at least 24 months. Infusion set compatibility and stability testing was performed using the same materials intended for the conduct of the clinical study.

Placebo

Placebo solution will be stored at room temperature within the study site pharmacy.

4.2 Acquisition

The Sponsor will provide the Investigator and clinical unit with adequate quantities of AV-1 and placebo. AV-1 will be stored and shipped from the AbViro-specified distribution center to the clinical site. Once received, AV-1 will be stored in the study site pharmacy and dispensed by the study site pharmacy to the study site staff. Unused product may be destroyed.

4.3 Preparation and Administration of Investigational Product

The IP will be aseptically prepared as per the pharmacy manual by delegated unblinded pharmacy personnel in INTRAVIA bags with pre-primed infusion set with a blunt tip cannula prior to IV infusion.

AV-1 will be diluted to the appropriate dose in sterile 0.9% NaCl. Diluted AV-1 should be clear and colorless.

The IP will be administered on the morning of Day 1 as a single IV infusion at planned nominal doses of 30, 90, 250, 500, and 1000 mg delivering the full product volume in 60 minutes. The exact dose will be determined following a safety data review after each cohort.

Complete instructions for the preparation of the IP are described in the pharmacy manual.

4.4 Accountability Procedures for the Investigational Product

The FDA requires accountability of the IPs. The pharmacist is responsible for ensuring that a current record of IP accountability is maintained, and that the IP is dispensed only at an official clinical site by authorized personnel as required by applicable regulations and guidelines. Records of IP accountability will consist of the date received, date administered, quantity administered, and the subject number to whom the drug was administered.

The pharmacist will be responsible for maintaining accurate records of the shipment and dispensing of the IP. The pharmacy records must be available for inspection by the Division of Microbiology and Infectious Diseases (DMID) monitoring contractors and is subject to inspection by a regulatory agency (eg, the FDA) at any time. An assigned blinded study monitor will review the pharmacy records.

Unused AV-1 vials will be stored upright at 2°C to 8°C in the study site pharmacy until clinical trial accountability is completed. At study termination, all unused AV-1 will be disposed of in accordance with the pharmacy manual.

5 SELECTION OF SUBJECTS AND STUDY ENROLLMENT AND WITHDRAWAL

5.1 Eligibility Criteria

Eligible subjects unable to participate in the study due to a scheduling conflict or if the group they are screening for has completed enrollment may be rescreened for participation in a later group.

A subject who has failed screening may also be rescreened for participation in a later group at the discretion of the Investigator and with Sponsor agreement based on the following criteria:

- 1. In the opinion of the Investigator, the parameter value does not represent a chronic condition that otherwise will preclude the volunteer from enrolling in the study; and
- 2. In the opinion of the Investigator, the abnormality is not likely to recur.

Tests that do not allow for a rescreen include the following:

- Positive human immunodeficiency virus, hepatitis B surface antigen, or hepatitis C virus antibody
- Positive flavivirus screen
- Positive urine drug screen

In these cases, a new screening number must be assigned for each subject who is rescreened, and a new informed consent form (ICF) must be signed.

5.1.1 Inclusion Criteria

Each volunteer must meet all the following criteria to be enrolled in this study:

- 1. Is a male or nonpregnant, nonlactating female, of any race, between 18 and 55 years of age, inclusive, at Screening.
- 2. Has a body mass index between 18.5 and 29.9 kg/m², inclusive, at Screening.
- 3. Is in good health at Screening and reaffirmed on Day -1.
 - a. Good health is defined by the absence of a medical condition described in the exclusion criteria and based on screening medical history, physical examination, vital signs, and 12-lead ECG.
 - b. If the subject has another current, ongoing chronic medical condition, the condition cannot meet any of the following criteria:

- I. First diagnosed within 3 months of enrollment; or
- II. A pre-existing medical condition that is not exclusionary but has worsened in terms of clinical outcome within 3 months of enrollment; or
- III. Involves need for medication that may pose a risk to the subject's safety or impede assessment of AEs or anti-AV-1 antibody response if they participate in the study.
- 4. Female subjects must have a negative serum beta-human chorionic gonadotropin pregnancy test at Screening and Check-in on Day –1 and, on admission to the unit, must not be lactating.
- 5. Female subjects must fulfill one of the following criteria as confirmed at Screening:
 - a. Postmenopausal women must have had ≥ 12 months of spontaneous amenorrhea with follicle-stimulating hormone concentration consistently ≥ 40 mIU/mL and must have a negative pregnancy test result at Screening and Check-in on Day -1.
 - b. Surgically sterile women, defined as those who have had a hysterectomy, bilateral ovariectomy (oophorectomy), or bilateral tubal ligation. Women who are surgically sterile must provide documentation of the procedure by an operative report or relevant medical records, and must have a negative pregnancy test result at Screening and Check-in.
 - c. Be willing to remain abstinent (not engage in sexual intercourse) from Check-in on Day -1 until the final follow-up visit on Day $120~(\pm 5)$.
 - d. Be willing to use one of the following acceptable methods of birth control until the final follow-up visit on Day 120 (±5): intrauterine device with spermicide; a female condom with spermicide; contraceptive sponge with spermicide; an intravaginal system (eg, NuvaRing®); a diaphragm with spermicide; a cervical cap with spermicide; or oral, implantable, transdermal, or injectable hormonal contraceptives beginning 3 months prior to dosing.
- 6. Male subjects who are biologically capable of fathering children must agree and commit to use of an adequate form of double-barrier contraception and refrain from sperm donation from Check-in on Day -1 until the final follow-up visit on Day 120 (±5). A male subject is considered capable of fathering children even if his sexual partner is sterile or using contraceptives.
- 7. Has not traveled outside the US within 60 days prior to Day -1 and agrees to not travel outside the US through the final follow-up visit on Day 120 (± 5).

8. Agrees to abide by the study restrictions and is willing to sign an ICF.

5.1.2 Exclusion Criteria

Volunteers meeting any of the following criteria will be excluded from the study:

- 1. Has any significant medical condition that, in the opinion of the Investigator or Sponsor, would interfere with the subject's ability to participate in the study or increase the risk of participating for that subject based on the investigator's brochure and the safety profile of AV-1.
 - a. Significant medical condition includes, but is not limited to, kidney disease with creatinine clearance <90 mL/min/1.73 cm² (CKD-EPI method), known active liver disease (including steatosis), ischemic heart disease, cardiac conduction disorder, chronic intestinal disease, hypertension (including treated), arrythmia requiring treatment, diabetes requiring insulin, neuropathy, myopathy, and malignancy (not including squamous cell skin cancer, basal cell skin cancer, or cervical low-grade squamous intraepithelial lesions).
 - b. Congenital nonhemolytic hyperbilirubinemia syndromes (eg, Gilbert's syndrome) are not acceptable.
- 2. Has one or more symptoms of a urinary tract infection (eg, dysuria, frequent, urgency, or suprapubic pain) at Screening or Check-in on Day –1.
- 3. Has a 12-lead ECG with:
 - a. Any clinically important abnormalities in rhythm, conduction, or morphology of the resting ECG and any clinically important abnormalities in the 12-lead ECG that, in the Investigator's opinion, may interfere with the interpretation of QTc interval changes, including abnormal ST-T-wave morphology.
 - b. QT interval corrected by Fridericia's formula (QTcF) of >450 msec in men or >460 msec in women.
 - c. PR > 220 msec.
 - d. Second or third degree atrioventricular block or atrioventricular dissociation.
 - e. Complete left or right bundle branch block.
 - f. Ventricular or atrial premature contractions in couplets or higher in grouping.
- 4. Has abnormal laboratory values for any of the hematology, serum chemistry, coagulation, or urinalysis tests outlined in Section 7.2.1 at Screening or Check-in on Day −1.

- 5. Is positive for hepatitis B surface antigen, hepatitis C virus antibody, or human immunodeficiency virus antibody types 1 and 2 within 35 days of enrollment.
- 6. Has any psychiatric condition or history of psychiatric condition that, in the opinion of the Investigator or Sponsor, would interfere with the subject's ability to participate in the study or increase the risk of the participation for that subject.
- 7. Is unwilling to abstain from alcohol, caffeine-, or other xanthine-containing foods or beverages, tobacco or nicotine-containing products, and all bergamottin-containing fruits and fruit juices (eg, Seville-oranges, grapefruit or grapefruit juice, pomelos, pomegranate or pomegranate juice, cranberry or cranberry juice) 72 hours prior to Day –1 and through discharge on Day 5.
- 8. Is unwilling to abstain from strenuous exercise 7 days before Day –1 through Day 15.
- 9. Has a history of alcoholism or drug/chemical abuse within 6 months prior to Day –1.
- 10. Has excessive alcohol consumption (regular alcohol intake >21 units per week for male subjects and >14 units of alcohol per week for female subjects) (1 unit is equal to approximately ½ pint [200 mL] of beer, 1 small glass [100 mL] of wine, or 1 measure [25 mL] of spirits).
- 11. Has a positive urine drug screen at Screening or Check-in on Day −1.
- 12. Has a positive cotinine urine test at Check-in on Day -1.
- 13. Has any confirmed or suspected immunosuppressive or immunodeficient condition, including, but not limited to, human immunodeficiency virus infection, or use of anti-cancer chemotherapy or radiation therapy (cytotoxic) in the 3 years prior to Screening.
- 14. Provides verbal history of vaccination with a licensed or investigational flavivirus vaccine for any of the following diseases: Zika virus, DENV, yellow fever virus, Japanese encephalitis virus, West Nile virus, St. Louis encephalitis virus, or tick-borne encephalitis virus or reportedly diagnosed with a flavivirus infection or disease.
- 15. Plans to receive a licensed flavivirus vaccine or participate in a flavivirus vaccine trial during the study.
- 16. Is positive for DENV or West Nile virus by immunoglobulin M, or immunoglobulin G, or Zika by immunoglobulin M serology testing within 35 days of enrollment.
- 17. Has a history of significant hypersensitivity, intolerance, or allergy to any drug compound, food, or other substance, unless approved by the Investigator (or designee).

- 18. Has had major surgery within 3 months prior to Screening or plans to have a major surgery during the study through the final follow-up on Day 120 (± 5).
- 19. Has been previously treated for a medical condition with a licensed monoclonal or polyclonal antibody any time in the past.
- 20. Has been dosed in a clinical study involving administration of an investigational monoclonal or polyclonal antibody in the 18 months (550 days) prior to IP administration on Day 1.
- 21. Has received an investigational drug within 28 days of IP administration on Day 1.
- 22. Has used any prohibited medication within 30 days prior to Day –1 or plans to use prohibited medication during the study.
 - a. Prohibited medications include immunosuppressive drugs, immune modulators (except acetaminophen), oral corticosteroids, inhaled or intranasal steroids (<800 µg/day beclomethasone is acceptable), and anti-neoplastic agents. Topical steroids are acceptable.
- 23. Has received or plans to receive any live vaccination, experimental or otherwise, within 28 days prior to or after Day 1; and receipt or planned receipt of an inactivated vaccination (or any COVID-19 vaccine), experimental or otherwise, within 14 days prior to or after Day 1.
- 24. Has received blood products within 60 days prior to Day –1.
- 25. Has donated or lost more than 450 mL of blood or plasma within 56 days of IP infusion on Day 1. The subject must also agree to refrain from donating blood or plasma during the study.
- 26. Has poor peripheral venous access.
- 27. Has previously completed or withdrawn from this study.
- 28. Is a current study site staff paid entirely or partially by the contractor for this trial, or staff who are supervised by the Investigator or subinvestigators.
- 29. In the opinion of the Investigator (or designee), the subject is not suitable for entry into the study.

5.2 Withdrawal from the Study, Discontinuation of Investigational Product, or Study Termination

5.2.1 Withdrawal from the Study or Discontinuation of the Investigational Product

Subjects are free to withdraw from the study at any time upon request. Subject participation in the study may be stopped at any time at the discretion of the Investigator or at the request of the Sponsor.

The Sponsor will be notified in advance whenever possible if subjects are stopped at the discretion of the Investigator. When a subject withdraws from the study or is stopped, the reason(s) are to be recorded by the Investigator on the relevant page of the electronic case report form (eCRF). Whenever possible, any subject who withdraws or is stopped from the study prematurely will undergo all ET assessments. Any subject who fails to return for final assessments will be contacted by the clinical site in an attempt to have them comply with the protocol. The status of subjects who fail to complete final assessments will be documented in the eCRF.

The reasons for stopping subject participation by the Investigator or Sponsor include, but are not limited to the following:

- The subject meets individual halting criteria (Section 8.6.2).
- Subject noncompliance based on any of the following criteria after IP administration and before completion of all follow-up visits through Day 120 (±5):
 - Positive urine drug screen
 - Has major surgery
 - Received another IP
 - Uses prohibited medication
 - Receives blood products or donates blood or plasma
- An AE or new clinical finding(s) for which continued participation, in the opinion of the Investigator, might compromise the safety of the subject, interfere with the subject's successful completion of this study, or interfere with the evaluation of responses.
- The subject is lost to follow-up.
- Subjects becoming pregnant prior to or following IP administration prior to the final follow-up visit on Day 120 (±5). Subject becoming pregnant after IP administration will not be included in data analysis but will be followed for safety.

If the subject consents, every attempt will be made to follow all AEs through resolution including those subjects that elect to withdraw. The procedures that collect safety data for the

purposes of research must be inclusive in the original ICF or the Investigator may seek subsequent informed consent using an IRB-approved consent form with the revised procedures.

The Investigator will inform the subject that already collected data will be retained and analyzed even if the subject withdraws from this study.

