2.3 Potential Risks and Benefits

2.3.1 Potential Risks

No clinical trials in humans have been conducted. Nonclinical GLP-compliant safety studies have indicated no safety concerns. However, as this is a first-in-human for AV-1, unexpected adverse events (AEs) are possible in humans.

Potential theoretical risks associated with the clinical evaluation of AV-1 in humans include immune reactions to AV-1 or its excipients or unintended adverse effects related to the specificity of the antibody. Potential AEs may occur immediately following infusion or be delayed and may range from mild to severe.

Consideration to these potential risks was included in the design of both the AV-1 product and the first-in-human clinical study. Subjects will be screened to ensure enrollment of only healthy adult subjects without significant underlying medical issues or history of hypersensitivity.

AV-1 is a fully human mAb that reduces the risk of immunogenicity-related complications. Additionally, subjects will receive only a single dose of AV-1, further limiting risk of immunogenicity more likely to result from repeated exposures. A single dose will also limit exposure and allow reversibility of any treatment-related adverse effects. The initial fixed starting dose of 30 mg allows for a >90-fold safety margin based on nonclinical data based on the FDA guidance (DHHS 2005). Sentinel dosing will be employed for each dose level to further limit the impact of unforeseen drug-related adverse safety outcomes.

Risk of acute reactions will be managed through close monitoring of subjects during and following administration of the investigational product (IP) infusion. Subjects will be admitted and remain in the clinical site beginning the day prior to the IP infusion (Day -1) through discharge on Day 5 to allow for regular monitoring for hypersensitivity and both laboratory or systemic adverse effects of IP dosing. Eight planned outpatient visits will follow subjects for approximately $120 \ (\pm 5)$ days after dosing to afford an appropriate amount of time to observe delayed AV-1-related AEs prior to subject completion of the study. Review of cumulative safety data will be performed prior to dose escalations.

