8.2 Specification of Safety Parameters

Safety will be assessed by the frequency and severity of:

- Occurrence of SAEs from the administration of AV-1 to final follow-up visit on Day 120 (±5).
- Occurrence of unsolicited AEs from the administration of AV-1 to the final follow-up visit on Day 120 (±5).
- Occurrence of solicited AEs from the administration of AV-1 to Day 8.

- Occurrence of changes from baseline in physical examination, vital sign measurements, and clinical safety laboratory values from the administration of AV-1 to the final follow-up visit on Day 120 (±5).
- Occurrence of changes from baseline in ECG parameters in the 48 hours after starting the AV-1 infusion and at Days 8 (+2), 43 (\pm 3), 85 (\pm 5), and 120 (\pm 5).

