8.6.2 Halting Criteria for Subject Infusions

The Investigator and study site staff must carefully observe the subjects for any AE during the infusion.

The infusion will be halted for an individual subject and will not resume if any of the following manifestations occur during the 1-hour infusion:

- Occurrence during dosing that, in the opinion of the Investigator, results in the inability to have confidence that the intended dose of IP was delivered.
- Infusion-related reaction of Grade 2 or higher.

In case of a suspected infusion-related reaction, at the discretion of the Investigator, the infusion rate may be slowed from a rate of 250 mL/hour to a rate of 125 mL/hour for symptom management. The infusion may also be stopped. The subject will be observed to determine the severity of the reaction for a period of up to 15 minutes. Depending on the assessment of the subject, supportive care can be administered, and the infusion may permanently be stopped. If the Investigator determines that there is no infusion reaction, no ongoing supportive care is required after dosing is stopped, or if the symptoms of the clinical reaction have been improved after 15 minutes, the infusion may be restarted. The decision to

continue the infusion is based on the assessment by the Investigator. The infusion will be halted if there is a reoccurrence after a pause in dosing.

- Symptomatic low blood pressure of <90 mm Hg systolic or >30% decrease from baseline in systolic or diastolic blood pressure at predose.
- Confirmed tachycardia with an increase in resting heat rate to ≥130 beats per minute (bpm), or development of ventricular dysrhythmia, or bradycardia (<45 bpm, or <40 bpm in subjects with baseline of <60 bpm) associated with complaints of dizziness, nausea, or feeling faint.
- Syncope.
- Confusion.
- Suspected Grade 3 AE or SAE.

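### Section 5.2.1 lets participation end after the only dose, and nothing keeps a stopped subject on the scheduled visits to Day 120

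*Protocol*

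**What the plan says.** Protocol 2.3.1 states that "subjects will receive only a single dose of AV-1". Protocol 5.2.1 allows the Investigator, at discretion, or the Sponsor, on request, to stop a subject's participation. Its list of reasons includes:

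- meeting the individual halting criteria of Section 8.6.2;
- "Subject noncompliance based on any of the following criteria after IP administration and before completion of all follow-up visits through Day 120", the criteria being a positive urine drug screen, major surgery, another IP, prohibited medication, and receipt of blood products or a blood or plasma donation;
- "An AE or new clinical finding(s) for which continued participation, in the opinion of the Investigator, might compromise the safety of the subject", or might interfere with completing the study or evaluating responses.

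Section 8.6.2 is an infusion rule: "The infusion will be halted for an individual subject and will not resume if any of the following manifestations occur during the 1-hour infusion". One of its triggers is "Infusion-related reaction of Grade 2 or higher"; others include syncope, confusion and a suspected Grade 3 AE or SAE. It does not mention leaving the study. On medication, exclusion criterion 22 in Section 5.1.2 says: "Prohibited medications include immunosuppressive drugs, immune modulators (except acetaminophen), oral corticosteroids", among others. Section 7.1.5.2 allows any drug needed for the subject's welfare and leaves continuation to a joint decision of Investigator and Sponsor.

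For stopped subjects, 5.2.1 provides the ET assessments where feasible, contact with those who do not return, and follow-up of AEs to resolution with consent. Pregnancy is the only listed reason for which it adds that the subject will be followed for safety. Section 8.2 defines the safety window as "Occurrence of unsolicited AEs from the administration of AV-1 to the final follow-up visit on Day 120", and the same window applies to SAEs.

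**The concern.** Where dosing is repeated, stopping a subject can protect that subject from further exposure. Here there is no further dose, so what ends is observation. Some of the listed reasons are safety outcomes or may follow from one: a halted infusion, an AE, or an oral corticosteroid given for a reaction. If those subjects leave the schedule, the people observed for less time are partly selected by how they responded to the infusion.

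The primary endpoints are safety endpoints. Section 2.3.1 justifies the eight outpatient visits as time to observe delayed AEs, and the escalation-halting counts in Section 8.6.1 run for the whole study. SAP 10.1 takes percentages over all subjects in the safety population, with no adjustment for time observed. A subject seen for three weeks therefore counts in the denominator like one seen for 17. Scheduled post-dose antibody samples fall only on Days 29, 85 and 120 (Section 7.2.3), so a subject stopped before Day 29 leaves at most one early ET sample.

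**Working it through.** **The plan's own figure.** 5 cohorts × (6 AV-1 + 2 placebo) = 40, as stated in Protocol 10.2. There is no hypothesis test and no power calculation to reproduce. Neither document gives an expected stopping rate, so the figures below are illustrations and not estimates of bias.

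**1. What each section ends.**

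| Place | What stops | What continues |
|---|---|---|
| Protocol 8.6.2 | The infusion | Not stated; leaving the study is not mentioned |
| Protocol 5.2.1 | Participation (discretionary) | ET visit where feasible; AEs to resolution with consent |
| Protocol 7.1.5.2 | Nothing automatically | Joint decision, case by case |
| Protocol 8.4 | – | AEs from first recognition to resolution, beyond the last visit if needed |

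No row keeps a stopped subject on the remaining scheduled visits. Section 8.4 starts from recognition of an event, so it covers known events and does not look for new ones. For a stop on Day 1, up to eight visits (Days 8 to 120) can become one ET visit.

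**2. Follow-up lost by a stop at Day 22** (a scheduled drug-screen visit), taking the ET visit as held that day.

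- Days lost: 120 − 22 = 98, of 120 − 1 = 119; 98/119 = 82%.
- Share of a six-subject dose group's follow-up: 98/(6 × 119) = 98/714 = 13.7%.

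**3. Chance of seeing a delayed event.** Assume a true delayed-event rate p, that stopping is unrelated to risk, and that stopped subjects contribute nothing later. Then P(at least one) = 1 − (1 − p)^n, and the one-sided 95% upper bound after 0/n is 1 − 0.05^(1/n).

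| Followed, of 6 | p = 5% | 10% | 20% | 30% | Bound for 0/n |
|---|---|---|---|---|---|
| 6 | 26.5% | 46.9% | 73.8% | 88.2% | 39.3% |
| 5 | 22.6% | 41.0% | 67.2% | 83.2% | 45.1% |
| 4 | 18.5% | 34.4% | 59.0% | 76.0% | 52.7% |

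If stopping is instead related to reaction, suppose 2 of 6 subjects truly have a delayed event (33.3%). With the denominator kept at 6, missing one gives 1/6 = 16.7%, and missing both gives 0/6.

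**4. PK.** The documents give no half-life. Assume a bi-exponential profile with equal weights, a 1-day initial half-life and a terminal half-life of T days, and a last sample 21 days after dosing. The 1-day phase is negligible by then, so the extrapolated fraction is about T × 2^(−21/T) / (1 + T).

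- T = 7: 7 × 0.125/8 = 11%
- T = 14: 14 × 0.354/15 = 33%
- T = 21: 21 × 0.5/22 = 48%
- T = 28: 28 × 0.595/29 = 57%

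Protocol 10.4.3 and SAP 8.3 retain AUC0-∞ only below 0.20, read here as 20%. Under this model the limit is crossed at a terminal half-life of a little under 10 days (T = 9.5 gives 9.5 × 0.216/10.5 = 19.5%). A later ET sample lowers the fraction: at 28 days post-dose with T = 21 it is 21 × 0.397/22 = 38%.

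**The case against.** A reader might infer that safety follow-up is simply lost for these subjects. The documents do not support that. Stopping is permitted, not required, and a steroid given for a reaction leads to a joint decision, not to automatic removal. The EOS/ET column of Appendix A includes examination, vital signs, ECG, laboratory tests, PK and antibody sampling. Known AEs are followed to resolution, related SAEs are reportable after the study ends (Section 8.3.1), and collected data are kept and analyzed. The SAP safety population takes in anyone given any amount of IP, a change from the protocol that SAP Section 11 declares, so partly dosed subjects stay in the summaries. All of this stands. What remains exposed is scheduled surveillance for new events.

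A reader might also infer that every listed reason selects subjects who reacted. Nothing in the documents links a positive drug screen, another IP or blood donation to a reaction, and little links major surgery to one. The Day 22 example is of this kind: it shows how much data can go, not informative loss.

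Nor is loss of AUC0-∞, CL and Vz established; it depends on the half-life and on the ET date. It does not apply to permanently halted infusions, because both documents already limit the PK population to subjects given the full AV-1 dose. Finally, the replacement rule in 5.2.2 speaks of subjects who withdraw. Applying it to stopped subjects is an interpretation, and it does not delete a replaced subject's safety data.

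Discretion does not close the gap. A decision to stop that rests on what happened after dosing can still be informative, and keeping a subject in the denominator does not restore missing observations.

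**Conclusion.** The point holds in this limited form. Section 5.2.1 does not separate halting an infusion, or a post-dose deviation, from ending follow-up, and neither document keeps a stopped subject on the schedule to Day 120. For halted infusions, AEs and some prohibited medication, the truncation could be informative and could bias AE incidence downward. For the other reasons it is mainly avoidable loss of safety, antibody and PK data.

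The size is unknown, because it depends on how often the discretion is used. On the assumptions shown, losing one or two of six subjects lowers the chance of seeing a delayed event with a true rate of 20% from 73.8% to 67.2% or 59.0%. A Day 22 stop leaves 11% to 57% of AUC extrapolated for terminal half-lives of 7 to 28 days, so loss of AUC0-∞ is conditional. This should be changed because it bears on the primary endpoint and costs little; it does not show that the planned safety analysis is invalid.

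**What to change.** Reconcile Protocol 5.2.1 with 8.6.2 and 7.1.5.2. Add to 5.2.1 that, once a subject has received any IP, meeting an infusion-halting criterion, an AE or a listed noncompliance is recorded (as a deviation where applicable) but does not by itself end follow-up. The safety and antibody visits already scheduled, and PK visits where the subject is evaluable, then continue to Day 120 unless the subject withdraws consent or the Investigator judges continued attendance unsafe. This leaves the infusion-halting criteria and the medication rules untouched.

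In the SAP, state that PK and antibody samples taken after such an event are flagged, and say whether they are left out of summaries or shown in a sensitivity listing.

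The cost is about one sentence in the protocol and one in the SAP, using visits already planned. The downside is that some data after the event will be confounded, for example by a corticosteroid or another IP, and will need that flag.
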